Analysis plan for Safety Use of Antipsychotics in Youth (SUAY)

Title: Safer Use of Antipsychotics in Youth (SUAY)

NCT: NCT03448575

Dated: 11/23/2022

Last updated: 12/17/2021

Analysis plan for Safety Use of Antipsychotics in Youth (SUAY)

Please indicate name and date for any changes in this document.

Last Edited: 05/24/2021 [name], [name], [name],
10/05/2021 & 12/17/2021 [name]

Title: A Pragmatic Effectiveness Trial: Safer Use of Antipsychotics in Youth (SUAY)

General Scientific Aim

The SUAY trial aims to minimize use of antipsychotics to treat non-psychotic behavioral disturbances in children in four real-world health care systems.

Specific Scientific Aim(s)

Our primary outcomes are percent of patients taking antipsychotic medication at 6 months post enrollment and total person-months of antipsychotic use by youth, based on medication order data. As a sensitivity analysis, we will also compare the percent of patients taking antipsychotic medication at 6 months post enrollment and total person-months of antipsychotic use by youth, based on prescription fill data.

Outcomes (dependent variable) of interest

Primary

- i. % of patients taking antipsychotic medications (provider orders) at 6 months post enrollment
- ii. Days of antipsychotic medication use (provider orders) during 6 months following enrollment

Secondary

- i. Emergency department/urgent care visit frequency, both for psychiatric crises and for other reasons;
- ii. Percentage of baseline and follow-up safety assessments (i.e., BMI measurement and laboratory orders);
- iii. Percentage of clinicians with at least one change in AP treatment (AP discontinuation, treatment adjustment, and therapy referral);
- iv. Modal stage at departure from algorithm (first line, second line, third line treatment prior to antipsychotic);
- v. Last stage of patient treatment status
- vi. Percent of patients that agree to behavioral health (BH) navigation;
- vii. Percentage of patients attending two or more system-provided therapy sessions;
- viii. Number of patients with any AP order

Predictor of interest: Treatment type (Intervention or Control)

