groupn	Randomization Group - use for descriptive stats (Intervention (1)/Control(2))	present
group_cat	Randomization Group - use in models (Control (0)/Intervention (1))	present
bmi_baseline	0 = no, 1 = yes, 8 = NA	absent
bmi_fu	0 = no, 1 = yes, 8 = NA	absent
bmi_both	If bmi_baseline AND bmi_fu = 1, then 1 = yes, otherwise 0 = no; if no AP order on randomization date, then 8 = NA.	absent
lipids_baseline	0 = no, 1 = yes, 8 = NA	absent
lipids_fu	0 = no, 1 = yes, 8 = NA	absent
lipids_both	If lipids_baseline AND lipids_fu = 1, then 1 = yes, otherwise 0 = no; if no AP order on randomization date, then 8 = NA.	absent
chl_baseline	0 = no, 1 = yes, 8 = NA	absent
chl_fu	0 = no, 1 = yes, 8 = NA	absent
chl_both	If chl_baseline AND chl_fu = 1, then 1 = yes, otherwise 0 = no; if no AP order on randomization date, then 8 = NA.	absent
hb1ac_baseline	0 = no, 1 = yes, 8 = NA	absent
hb1ac_fu	0 = no, 1 = yes, 8 = NA	absent
hb1ac_both	If hb1ac_baseline AND hb1ac_fu = 1, then 1 = yes, otherwise 0 = no; if no AP order on randomization date, then 8 = NA.	absent
prolactin_baseline	0 = no, 1 = yes, 8 = NA	absent
prolactin_fu	0 = no, 1 = yes, 8 = NA	absent
prolactin_both	If prolactin_baseline AND prolactin_fu = 1, then 1 = yes, otherwise 0 = no; if no AP order on randomization date, then 8=NA.	absent
any_lab_baseline	0 = no, 1 = yes, 8 = NA	absent
any_lab_fu	0 = no, 1 = yes, 8 = NA	absent
any_lab_both	If any_lab_baseline AND any_lab_fu = 1, then 1 = yes, otherwise 0 = no; if no AP order on randomization date, then 8=NA.	absent

Secondary analysis III

Percentage of clinicians with at least one change in AP treatment (defined as AP discontinuation, treatment adjustment (change in other psychotropic medication), and therapy referral);

Definition: At least one of the following must occur to be flagged as 'Yes' or assigned the number 1

- AP discontinuation: no refills
- Medication adjustment i.e. non-AP mental health adjustment (either of the two below or both) by provider within 60 days of patient enrollment in study:
 - adding new psychotropic medication (including switching medications)
- Therapy referral by provider within 60 days of patient enrollment in study.
 - any new psychotherapy i.e. referral
- New mental health diagnosis (issued by the same provider) within 60 days of patient enrollment in study.

Analysis plan for Safety Use of Antipsychotics in Youth (SUAY)

- At least one AP treatment change

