Descriptive analysis will summarize **the percent of** clinicians with each type of change and at least one change in AP treatment (AP discontinuation, treatment adjustment, therapy referral, and new diagnosis), defined above.

Inferential analysis: We will estimate the **odds ratio (OR) of at least one change in AP treatment**, between intervention and control. Binary treatment arm assignment and prior hospitalization will be the only covariate included in the regression model and the estimated coefficient is interpreted as the log-OR of observing at least one change in AP treatment, for an intervention patient vs. a control patient. Patient is the unit of analysis, GEE will be used to account for correlation within provider, and robust standard errors will be calculated to construct a 95% CI around the estimated OR. Our null hypothesis is that the OR is equal to 1, corresponding to no statistically significant difference between the AP treatment, for the treatment arms. We will reject the null hypothesis if the lower bound of the 95% CI is above 1 (increased change in AP treatment in treatment arm) or the upper bound is below 1 (decreased change in AP treatment in treatment arm).

Variables	Definition	Present/Absent
groupn	Randomization Group – use for descriptive stats (Intervention (1)/Control(2))	present
group_cat	Randomization Group – use in models (Control (0)/Intervention (1))	present
prior_hosp	Prior Hospitalization (No (0)/Yes(1))	present
no_refill	if there exists a rdate < rxdate for AP <= enddate or disenrollmentdate, then 0 = no, otherwise 1=yes	absent
new_med	0 = no new medication within [rdate, rdate + 60 days], 1 = at least one new medication within [rdate, rdate + 60 days]	absent
th_referral	0 = no new psychotherapy visit observed within [rdate, rdate + 60 days], Otherwise, 1 = at least one new psychotherapy visit	absent
new_mh_dx	0 = no new mental health diagnosis, 1 = at least one new mental health diagnosis	absent
trt_change	If no_refills, new_med, th_referral, and new_mh_dx = 0, 0 = no AP treatment change, Otherwise 1 = at least one AP treatment change	absent

Secondary analysis IV

Modal stage at departure from algorithm (first line, second line, third line treatment prior to antipsychotic);

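### Secondary analysis III is named by three treatment components but tested on a composite that also counts a new diagnosis, and its variable table drops limits that the text sets

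*SAP*

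**What the plan says.** The SAP describes this outcome in four places.

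- **Outcome list** (Outcomes of interest, Secondary iii): "Percentage of clinicians with at least one change in AP treatment (AP discontinuation, treatment adjustment, and therapy referral". Three components.
- **Heading of Secondary analysis III**: "defined as AP discontinuation, treatment adjustment (change in other psychotropic medication), and therapy referral". The same three, with treatment adjustment explained.
- **Definition bullets and descriptive paragraph of Secondary analysis III**: a fourth component is added, "New mental health diagnosis (issued by the same provider) within 60 days of patient enrollment in study". The descriptive paragraph then lists "AP discontinuation, treatment adjustment, therapy referral, and new diagnosis" and plans to summarise each type as well as the composite.
- **Variable table of Secondary analysis III**: the composite `trt_change` uses all four flags, "If no_refills, new_med, th_referral, and new_mh_dx = 0, 0 = no AP treatment change", and is 1 otherwise.

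For medication, the bullet reads "Medication adjustment i.e. non-AP mental health adjustment (either of the two below or both) by provider within 60 days of patient enrollment in study". Only one form follows: "adding new psychotropic medication (including switching medications". The table codes `new_med` as "1 = at least one new medication within [rdate, rdate + 60 days" (the window closes there), with no restriction on drug class or prescriber. `new_mh_dx` is coded as any new mental health diagnosis, with no time window and no provider condition.

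The inferential paragraph tests only the composite and interprets the coefficient as the log odds ratio of at least one change in antipsychotic treatment.

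**The concern.** The label and the tested variable do not match. A diagnosis code is not a change of treatment, and neither the SAP outcome list nor the section heading includes it. If diagnoses are recorded at different rates in the two arms, the odds ratio can depart from 1 when no treatment differs. If they are recorded equally, the component adds events unrelated to the effect and pulls the odds ratio towards 1.

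A route to unequal recording exists in the design. In the intervention arm a child and adolescent psychiatrist reviews each case, diagnoses included, and feedback goes to the prescriber every time (Protocol 7.3 and 7.3.1). Control prescribers have no such review (Protocol 5.5). Whether this changes diagnostic coding is not stated.

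The loose coding of `new_med` is a separate problem. If programmed as the table reads, it could leave almost no patient scored 0, and the comparison would carry little information.

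**Working it through.** The plan states no rate, odds ratio or power for this outcome, so there is no figure to reproduce. The check is a comparison of definitions, then an illustration on assumed rates.

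**1. Component lists side by side**

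| Place in SAP | Discontinuation | Other psychotropic change | Therapy referral | New diagnosis |
|---|---|---|---|---|
| Outcome list | yes | yes | yes | no |
| Secondary III heading | yes | yes | yes | no |
| Secondary III bullets | yes | yes | yes | yes |
| Descriptive paragraph | yes | yes | yes | yes |
| `trt_change` | yes | yes | yes | yes |

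Take a patient with (`no_refill`, `new_med`, `th_referral`, `new_mh_dx`) = (0, 0, 0, 1). The first two rows score no change. The coded variable scores 1.

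**2. Limits in the bullets against the table**

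| Limit | Bullets | Table |
|---|---|---|
| Medication: non-antipsychotic | yes | absent |
| Medication: psychotropic | yes | absent |
| Medication: by the provider | yes | absent |
| Medication: 60 days | yes | yes, including the randomization date |
| Diagnosis: same provider | yes | absent |
| Diagnosis: 60 days | yes | absent |

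**3. Who can score 0 if the table is read literally**

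A new episode requires no outpatient antipsychotic order in the prior 180 days (Protocol 5.2), so an index antipsychotic is a new medication on day 0.

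- Antipsychotic on the randomization date: `new_med` = 1.
- None on that date and none later: `no_refill` = 1.
- None on that date, first one by day 60: `new_med` = 1.
- None on that date, first one after day 60: 0 only if there is also no other new drug by day 60, no new psychotherapy visit by day 60 and no new diagnosis.

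Only part of the last group scores 0, so the composite approaches 100% in both arms. This takes every index entry as a new medication. The SAP notes that patient-reported entries cannot be told apart from orders in Epic.

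**4. Illustration of the diagnosis component**

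Assumptions, none from the documents: a combined rate p on the three named components, a diagnosis rate d, and independence. Then composite = 1 − (1 − p)(1 − d), and the odds ratio is the ratio of the composite odds.

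*No difference on the three components (p = 50% in both arms):*

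- d = 20% vs 30%: 1 − 0.5×0.8 = 0.60 and 1 − 0.5×0.7 = 0.65. OR = (0.65/0.35)/(0.60/0.40) = 1.24.
- d = 20% vs 40%: 0.60 and 1 − 0.5×0.6 = 0.70. OR = (0.70/0.30)/(0.60/0.40) = 1.56.
- Across d = 10% vs 20%, 20% vs 30% and 20% vs 40%, the OR runs from 1.23 to 1.56. With p = 30% it runs from 1.32 to 1.76.

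Chance of rejecting the null with n = 360 per arm (Protocol 8.1), two-sided 5%, no allowance for clustering: Φ[(Δ − 1.96·SE₀)/SE₁], SE₀ pooled and SE₁ unpooled.

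- 0.60 vs 0.65: (0.05 − 1.96×0.0361)/0.0360 = −0.58, giving 28%.
- 0.60 vs 0.70: (0.10 − 1.96×0.0356)/0.0354 = 0.86, giving 80%.

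*True difference on the three components (50% vs 60%, OR 1.50), equal diagnosis rates:*

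- d = 10%: 0.55 vs 0.64, OR 1.45.
- d = 20%: 0.60 vs 0.68, OR 1.42.
- d = 40%: 0.70 vs 0.76, OR 1.36.

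*The same true difference, unequal diagnosis rates* (control d 10% to 40%, diagnosis odds ratio 0.5 to 2.0): the composite OR runs from 1.00 to 2.07. At the low end, d = 40% vs 25% gives 0.70 vs 1 − 0.4×0.75 = 0.70. At the high end, d = 40% vs 57.1% gives 0.70 vs 0.829.

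**The case against.** The strongest reply is that this is a documentation slip. The fourth component is openly listed in the bullets and the descriptive paragraph, and the bullets already contain the limits missing from the table. An analyst who treats the table as shorthand would not let the index antipsychotic set `new_med`. Each type of change is also summarised separately, so a reader could see whether diagnoses drive the composite. The outcome is secondary and unpowered, and no primary or non-inferiority conclusion depends on it.

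Much of this stands, and it limits the point. It does not remove it. The outcome list and heading still disagree with the tested variable, the test uses only the composite, and the table is what would be programmed.

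Some stronger readings are tempting, and the documents do not support them:

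- **That the odds ratio does not measure treatment change.** Three of the four flags do measure it; the result is a mixture.
- **That the plan defines medication adjustment as any new drug.** The text limits it to a non-antipsychotic psychotropic. The fault is a mismatch between text and table.
- **That psychiatrist review will inflate diagnoses in the intervention arm.** The protocol describes review and treatment feedback. It does not say that prescribers will code more diagnoses.
- **That stops and dose changes of other psychotropics are deliberately excluded.** Two forms are announced and one is listed; the second may have been lost. Switching is counted.

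The illustration also depends on independence. If new diagnoses occur only in patients who already have a treatment change, the composite equals the three-component rate and nothing is distorted.

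**Conclusion.** The concern holds in a limited form. Secondary analysis III carries two incompatible definitions, and under the coded one a new diagnosis alone counts as an antipsychotic treatment change. The variable table also drops stated limits. Followed literally, it makes the composite nearly universal in both arms.

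The definitional conflict is certain from the text. The numerical consequence is not: with no component rates in the documents, neither size nor direction can be known. The odds ratios above are illustrations that rest on assumed rates and independent components, and the rejection probabilities also ignore clustering by provider. The near-100% result applies only if the table is programmed without the text's restrictions. No odds ratio for this outcome appears in the documents; one is only planned.

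This should be corrected because the outcome has its own hypothesis test. It does not touch the primary analyses.

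**What to change.** 1. Build the tested `trt_change` from the three components named in the outcome list and the section heading.
2. Keep new mental health diagnosis only as the separate descriptive line already planned. If the four-component version is kept, relabel it so that it no longer claims to be treatment change, and report the three-component odds ratio beside it. Do the same if the analysis has already been run.
3. Code `new_med` as a new non-antipsychotic psychotropic ordered by the provider within 60 days of enrollment, excluding the index antipsychotic.
4. Apply the same-provider and 60-day limits to `new_mh_dx`.
5. State the second form of medication adjustment that the bullet announces, or correct the bullet to one form.

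The cost is a wording change and a little recoding; the SAP marks all the component and composite variables as absent, that is, not yet built. The composite percentage will probably be lower.

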We will compare the outcomes of patients initially prescribed an antipsychotic medication from intervention providers versus control providers. We plan to conduct an intent-to-treat analysis i.e. if a patient is enrolled when an intervention provider issues a qualifying prescription, the patient is enrolled in the intervention arm and, even if the patient sees a control provider at some point, the patient will remain in the intervention arm. Intervention arm is a binary treatment assignment that should be indicated for all enrolled patients in the analytic dataset.

Baseline Covariates

Baseline covariates for this study include: age, gender, race, ethnicity, site, type of insurance (Medicaid/Commercial/Other i.e. self-paid), any inpatient hospitalization in the prior year, provider type and new health plan enrollee (defined as person who does not have 2 or more encounters at least 60 days apart in the year prior to their prescription order date). This definition of new health plan enrollee will be compared to an alternate definition in the three sites with health plan enrollment data: < 105 days enrolled in the health care plan before randomization date). Note that gaps in enrollment less than 45 days count towards the total of 105. Gaps in enrollment ≥ 45 days do not count towards the total of 105, nor does any enrollment prior to the gap ≥ 45 days. Any inpatient hospitalization in the prior year (-1 to -365 days from randomization date) will be adjusted for in primary analyses as it is prognostic of the outcome and will increase precision.

Health plan enrollment and follow-up time

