Definition: To assess this outcome, we will take account of the treatment(s) patients had before the BPA fired i.e. before the randomization date. These treatments have already been categorized into first line, second line and third line in the consensus panel document endorsed by the study psychiatrists and used to make suggestions regarding treatment changes.

Descriptive analysis will summarize **the percent of patients with first line, second line or third line** treatment algorithm departure.

Analysis plan for Safety Use of Antipsychotics in Youth (SUAY)

No Inferential analysis will be done for this outcome.

Variables	Definition	Present/Absent
groupn	Randomization Group – use for descriptive stats (Intervention (1)/Control(2))	present
group_cat	Randomization Group – use in models (Control (0)/Intervention (1))	present
trt_line	0 = no treatment, 1 = first line, 2 = second line, 3 = third line	absent

Secondary analysis V (Intervention group only)

Last stage of patient treatment status

Definition: The last stage of patient treatment status takes accounts for patients when they stop at either the BPA firing, provider completed CAP consultation, navigation stage (consent status and number of calls), or tele-mental health (consent status and number of sessions)

Descriptive statistics will show the frequencies (sample size, percentages) of the last stage of patient treatment status at patient’s study completion, as well as the mean and standard deviation of calls and TMH sessions for participants with any navigation calls or TMH sessions, respectively.

No inferential analysis will be performed for this outcome.

Variables	Definition	Present/Absent
trt_stage	If CAP_completed = pending, 1 = BPA If CAP_completed = completed, 2 = CAP If nav_status = agreed, 3 = NAV_C If max(n_nav_calls_delivered) > 0, then 4 = NAV_D If TMH_status = agreed, 5 = TMH_C If max(n_TMH_delivered) > 0, then 6 = TMH_D	present
trt_stage_n_nav_calls_delivered	Number of navigation calls delivered	Present
trt_stage_n_tmh_delivered	Number of telemental health delivered	Present

Secondary analysis VI (Intervention Group Only)

Percent of patients that agree to behavioral health (BH) navigation

Descriptive analysis will summarize **the percent of patients that agree to behavioral health (BH) navigation**

No inferential analysis will be performed for this outcome.

Variables	Definition	Present/Absent
accepts_nav	If nav_status= agreed	present

Secondary analysis VII

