Percentage of patients attending two or more system-provided therapy sessions

Descriptive analysis will summarize **the percent of patients attending two or more system-provided therapy sessions**

Inferential analysis: We will estimate the **odds ratio (OR) of attendance to two or more system-provided therapy sessions between intervention and control.** The outcome will be

Analysis plan for Safety Use of Antipsychotics in Youth (SUAY)

binary: two or more sessions (outcome=1) vs. fewer than two sessions (outcome=0). Binary treatment arm assignment and prior hospitalizations will be the only covariate included in the regression model and the estimated coefficient is interpreted as the log-OR of attending two or more system-provided therapy sessions, for an intervention patient vs. a control patient. Patient is the unit of analysis, GEE will be used to account for correlation within provider, and robust standard errors will be calculated to construct a 95% CI around the estimated OR. Our null hypothesis is that the OR is equal to 1, corresponding to no statistically significant difference between attending system-provided sessions, for the treatment arms. We will reject the null hypothesis if the lower bound of the 95% CI is above 1 (increased attendance to two or more system-provided therapy sessions in treatment arm) or the upper bound is below 1 (decreased attendance to two or more system-provided therapy sessions, in treatment arm).

Variables	Definition	Present/Absent
groupn	Randomization Group – use for descriptive stats (Intervention (1)/Control(2))	present
group_cat	Randomization Group – use in models (Control (0)/Intervention (1))	present
prior_hosp	Prior Hospitalization (No (0)/Yes(1))	present
th_sessions	defined as patients attending at least 2 system-provided therapy sessions (visits) throughout the study period	present

Secondary analysis VIII

Note: Data harvesting was not completed and this analysis was not conducted due to time constraints.

- (i) Behavioral Change Analysis: Proportion of providers’ patients with any AP order after BPA exposure during the study
- (ii) Sustainment Analysis: Proportion of providers’ patients with any AP order, both during and after the study

Note that: Intervention BPA gets turns off and Control Arm BPA turns on for both groups (July 1, 2020)

Behavioral Change Analysis:

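### Secondary analysis VII leaves out therapy attendance before enrolment: the test is valid but probably less powerful than it could be

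*SAP*

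**What the plan says.** The outcome variable in SAP Secondary analysis VII, th_sessions, is "defined as patients attending at least 2 system-provided therapy sessions (visits) throughout the study period". The effect measure is an OR, and "robust standard errors will be calculated to construct a 95% CI around the estimated OR". On covariates the plan says "Binary treatment arm assignment and prior hospitalizations will be the only covariate included in the regression model". The variable table agrees: it lists arm, prior_hosp and the outcome, and nothing on therapy before enrolment.

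The SAP's Baseline Covariates section contains no prior-therapy measure either. It gives a reason for adjusting for hospitalization in the prior year: that variable "will be adjusted for in primary analyses as it is prognostic of the outcome and will increase precision". Secondary VII carries the same covariate over with no argument specific to therapy attendance.

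Two other secondary analyses rely on treatment history. Secondary III counts "any new psychotherapy i.e. referral" within 60 days of enrolment, which needs some way of telling new therapy from old. For Secondary IV, "we will take account of the treatment(s) patients had before the BPA fired i.e. before the randomization date". The variables concerned, th_referral and trt_line, are both marked absent, and no look-back is defined for new therapy.

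Protocol section 7.5 lists being in therapy already among the reasons for not offering bridging, so such patients are expected. No prevalence is given.

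**The concern.** Encouraging psychosocial therapy is a stated purpose of the trial (Protocol Summary), and Secondary VII is the SAP's between-arm test of whether patients attended it. Patients who were attending sessions before the alert can be expected to reach two sessions in either arm, whatever the intervention does. A model that ignores this treats a predictable part of the variation as noise.

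The two primary analyses have sensitivity analyses with further covariates. Secondary VII has none, so nothing elsewhere in the plan recovers the loss. At stake is the chance of detecting a real increase in therapy attendance.

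**Working it through.** **Inputs.** The documents give no rate, power or precision figure for Secondary VII, so there is no stated figure to reproduce. From the documents: n = 360 per arm (Protocol section 8.1, the upper figure remaining at 6 months). Assumed, because the documents are silent: control attendance 50%; half of patients in therapy at baseline (x = 1); treatment OR 1.6 conditional on x; prior-therapy OR of 2, 3, 6 or 10; independent patients; prior_hosp left out of the calculation; two-sided test at 0.05.

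**Formulas.** Write P(t,x) for the probability of attendance in arm t at baseline status x, with p0 and p1 the arm averages.

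- With 50% attendance and 50% prevalence, the control log-odds at x = 0 is −½ ln(prior-therapy OR).
- Without x: SE = √[1/(n·p0(1−p0)) + 1/(n·p1(1−p1))], and power = Φ(ln(marginal OR)/SE − 1.96).
- With x: let w(t,x) = (n/2)·P(t,x)(1−P(t,x)). The information is the sum over x of w(0,x)w(1,x)/(w(0,x)+w(1,x)), SE = 1/√information, and power = Φ(ln 1.6/SE − 1.96).
- Standardised risk difference (RD): variance = (1/2n) × the average over x of [2P(1,x)(1−P(1,x)) + 2P(0,x)(1−P(0,x)) + (P(1,x)−P(0,x)−RD)²].

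**Prior-therapy OR of 6, worked through.**

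1. Control probabilities are 0.290 (x = 0) and 0.710 (x = 1). Multiplying the odds by 1.6 gives 0.395 and 0.797 in the intervention arm, so p1 = 0.596. The marginal OR is 0.596/0.404 = 1.475, with log 0.3885.
2. Without x: SE = √(0.01111 + 0.01153) = 0.1505. Power = Φ(0.3885/0.1505 − 1.96) = Φ(0.62) = 73%.
3. With x: the weights are 37.05 and 43.02 at x = 0, and 37.05 and 29.16 at x = 1. The information is 19.91 + 16.32 = 36.22 (unrounded sum), so SE = 0.166. Power = Φ(0.470/0.1662 − 1.96) = Φ(0.87) = 81%.
4. Standardised RD: variance 0.8128/720 = 0.001129, against 0.4908/360 = 0.001363 unadjusted, which is 17% lower.

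**All scenarios.**

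| Prior-therapy OR | Marginal OR | SE of log-OR, without / with | Power, without / with | Variance reduction, standardised RD |
|---|---|---|---|---|
| 2 | 1.58 | 0.151 / 0.153 | 86% / 87% | 3% |
| 3 | 1.55 | 0.151 / 0.157 | 82.5% / 85% | 7% |
| 6 | 1.47 | 0.150 / 0.166 | 73% / 81% | 17% |
| 10 | 1.41 | 0.150 / 0.176 | 63% / 76% | 26% |

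Read across the rows, not down the columns. Unadjusted power falls down the table partly because fixing the conditional OR at 1.6 makes the marginal effect smaller.

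**Other assumptions.** With conditional OR 1.5 and both control attendance and prior-therapy prevalence between 30% and 50%, the power gain is about 1 point at prior-therapy OR 2, 4 to 5 at OR 4, 7 to 11 at OR 8, and 11 to 17 at OR 16. A simulation of 2,000 trials (OR 8, both rates 50%) gave power of 54.9% and 67.0%, against 55.4% and 65.9% by formula. The spread of the log-OR was 0.149 without and 0.171 with the covariate.

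**The case against.** **A reader might infer that the planned odds ratio is imprecise and that adding the covariate would narrow its interval.** It would not. In every row the SE of the log-OR rises, because the arm coefficient becomes a conditional OR, a different quantity and further from 1. The gain is in power. An interval narrows only for a standardised marginal effect. This part of the objection stands, and it means that adding the covariate alone would be an incomplete remedy.

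**A reader might infer that the analysis is biased.** Omitting a baseline covariate does not by itself bias a randomised comparison, and chance imbalance is reflected in the confidence interval. One plain model used across several outcomes is a legitimate choice.

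**A reader might infer that prior therapy is already in the dataset.** The documents do not show this. No such variable is listed, th_referral and trt_line are marked absent, and th_sessions covers the study period only. The reason for not offering bridging is recorded by navigators, who work with intervention patients only, so it cannot serve as a covariate. The SAP also notes that data harvesting for Secondary VIII was not completed. Derivation from visit records is plausible, since Secondary III and IV rest on treatment history, but it is extra work.

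**The size rests on assumptions.** This also stands. That earlier attendance predicts later attendance is an inference with no figure behind it in the documents, and at an OR of 2 the gain is only about 1 point. Provider clustering would change the absolute figures and possibly the gain.

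None of this removes the benefit. Incomplete look-back makes the covariate a weaker predictor, and so reduces the gain.

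**Conclusion.** The point holds as one of efficiency. Secondary VII is valid as planned, but it omits the baseline counterpart of its own outcome while adjusting for a variable chosen with the primary outcomes in mind. The probable cost is power: from about 1 point if prior therapy is a weak predictor (OR 2) to about 13 points if it is strong (OR 10), under the stated assumptions. Apart from the 360 per arm, none of the inputs comes from the documents, so these figures illustrate the loss and do not estimate it. The documents do not support reading this as bias or as an error in the planned odds ratio. It concerns one secondary outcome and does not touch the primary analyses.

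**What to change.** 1. Derive, in both arms and from the same visit records, system-provided therapy attendance in a fixed window before enrolment, for example any session, or two or more, in days −180 to −1. State the window and the threshold in the SAP.
2. Add it to the Secondary VII model beside arm and prior_hosp, keeping the GEE with provider-clustered robust standard errors.
3. Report a standardised marginal OR or risk difference: average the fitted probabilities under each arm over all patients, with an interval that respects provider clustering. The estimand then stays marginal over prior therapy, and its interval is the one expected to narrow.
4. Use new_enrollee_1 to flag patients whose look-back is incomplete, and note that therapy received elsewhere may go unseen, possibly more so at NCH, where the SAP says patients need not belong to a particular health plan.
5. If results are already known, keep the planned analysis as it is and report this as a labelled post hoc sensitivity analysis.

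The cost is one variable not currently listed in the SAP, a few sentences of text, and a standardisation step in the analysis code.
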